Pain reported during/following PDT will be assessed using an 11-point numeric rating pain scale (NRPS) assessment by the subject (see [Appendix C](#)). The assessed pain should be additionally documented in the eCRF. Further, the NRPS result indicated by the subject should be transformed for documentation in the AE eCRF page as follows: pain 1-3 = mild, 4-7 = moderate, 8-10 = severe.

If possible, each subject should be assessed by the same investigator(s)/staff personnel at each visit.

At each visit or during the phone contact(s) after the PDT sessions, subjects will also be asked if they have experienced any adverse reaction since their previous clinic visit using questions like "Have you noticed anything in the study surrounding areas since we last saw you?" Any signs or symptoms reported by the subject that correspond to one of the 10 local skin reaction categories and/or 3 local discomfort categories listed above should be scored for severity according to the subject's response to the following question: "How much, if any, difficulty or disruption has this (sign) caused you?"

Using the information provided by the subject, the clinical staff should record the most severe reaction reported by the subject in each category with start and stop date (if applicable) using the descriptors listed below:

- 0 = none (no reaction recalled by the subject)
- 1 = mild (the subject is aware of the signs and symptoms, but the signs and symptoms are well tolerated and do not interfere with daily activities)
- 2 = moderate (the signs and symptoms are sufficient to restrict, but not to prevent, usual daily activities for the subject)
- 3 = severe (the subject is unable to perform usual daily activities).

New lesions

Assessment of new lesions during the clinical observation period and the FU part of the study will include new NMSC and melanoma, as well as new AK lesions.

New lesions with indication of localization(s) and reference to the treatment field(s) should be reported as (S)AE. These new lesions may be treated during the clinical observation period with

physical measures at the discretion of the investigator and without restriction during the follow-up period. Please refer to [Section 6.2 Concomitant treatments for restrictions](#).

Physical examination

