11.3.4 Safety analyses

All secondary safety endpoints (see [Section 7.3.2](#) and [Section 11.1.6](#)) will be analyzed descriptively and in an exploratory way. These safety analyses will be performed for the SAF set.

AEs will be coded according to the latest Medical Dictionary for Regulatory Activities (MedDRA) version available at the day of database closure. The analysis will focus on the TEAEs. TEAEs will be summarized and tabulated according to primary system organ class and preferred term. TEAEs leading to death and TEAEs resulting in discontinuation of study will be tabulated using frequency tables if a reasonable number of AEs of this type are observed. The occurrence of any new lesions by type (AK, NMSC, and melanoma) will be tabulated using frequency tables.

A listing of subjects with AEs will be provided for all AEs reported and all subjects enrolled.

The frequency of local skin reactions at the treatment field and of local discomfort will be presented together with the respective CIs for each treatment group. The mean and the maximal pain score and the respective CIs will be presented for each assessment time point and treatment group.

All laboratory values will be classified as normal or abnormal according to the laboratory's normal ranges and indicated as CS or NCS by the investigator. Out of range laboratory values that are considered CS will be documented in the medical history (Visit 1) or as AEs (Visit 5 or Visit 8) and listed as such. Details of further analyses will be specified in the SAP.

The analyses of variables for vital signs will focus on the evaluation of the change from baseline to the scheduled time points after baseline. Descriptive analysis (number of subjects, mean, median and SD, minimum, maximum) of the time course and of changes from baseline to each post-baseline time point will be presented.

General physical examinations will include the following body systems: heart, lung, abdomen, nervous system, skin, musculoskeletal system, lymph nodes, limbs, head, ears, eyes, nose, throat, and others. All clinically significant abnormal physical findings will be listed. Details of further analyses will be specified in the SAP.

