#### Frequency and extent of TEAEs, including SAEs

TEAEs are defined as all AEs with time of onset on or after the time of treatment with randomized IMP within 4 weeks (28 days) after each PDT cycle. If time of onset of AEs is not within 4 weeks (28 days) after each PDT cycle, but is identified to be at least possibly related to IMP or medical device, AEs will be assumed as TEAEs. The reference dates will be calculated as date of last PDT within each PDT cycle + 28, i.e. date of PDT-2 and/or PDT-4, respectively. If PDT-2 and/or PDT-4 are not available, the dates of PDT-1 and/or PDT-3 will be used for calculation of reference dates. These reference dates will be used for assignment of TEAEs. If unclear due to incomplete start time/date of AE or PDT, AEs will be assumed as TEAEs, as far as end time/date of AE is not before first treatment in first PDT cycle. AEs and TEAEs will be summarized and tabulated according to primary system organ class and preferred term displaying the number of events as well as counts and percentages on a subject basis per treatment arm.

[figure not shown]
Additionally, TEAEs by sex, TEAEs by age group I, serious TEAEs and TEAEs by intensity (mild/moderate/severe/unknown) will be tabulated. Related TEAEs (defined as possibly, probably, or definitely related, or with missing relationship) will be presented by intensity overall (related to IMP or related to medical device), related to IMP only, related to IMP and medical device and related to medical device only. Additionally, TEAEs by relationship (unrelated / unlikely related / probably related / probably related / definitely related) will be presented related to IMP and related to medical device separately.

TEAEs leading to death and TEAEs resulting in discontinuation of study will be tabulated if more than 5 events are observed. Specification of any action taken documented on AE page as 'Withdrawal from study' will be used for detection of TEAEs resulting in discontinuation of study.

A listing of subjects with TEAEs will be provided for all TEAEs reported. Non-TEAEs, i.e. AEs with onset before treatment or later than 4 weeks after each PDT cycle, will be listed separately for all subjects enrolled. In listings, the start day of the AE relative to start of treatment will be calculated for complete start dates only. Duration of events is only calculated for complete start and end dates.

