#### Local discomfort

The frequency and exact 95% CIs for each proportion of local discomfort during PDT (illumination) (using a 4-point scale ranging from none (0) to severe (3) for each category: burning, itching, other) will be presented by category and for each assessment time point. Local discomfort per illumination field, i.e. per lesion location (body system) as well, is available. Worst intensity over all timepoints for each lesion location and category will be considered for tabulation. In case of both illumination fields have same location, worst intensity of both illumination fields will be considered for tabulation. Missing or unknown intensity will not be considered for worst intensity analysis. Additionally, binary variables for each lesion location and category will be created for presentation of 95% CIs. Variable will be 'yes' if corresponding discomfort is documented at least once over all timepoints for corresponding lesion location. Otherwise, variable will be 'no'. In case of both illumination fields have same location fields have same location, variable will be 'yes' if corresponding discomfort is documented at least once over all timepoints for corresponding lesion location. Otherwise, variable will be 'no'.

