#### Pain

Pain reported during PDT (illumination) will be assessed using an 11-point numeric rating pain scale (NRPS) assessment by the subject. Pain assessment per illumination field, i.e. per lesion location (body system) as well, is available. The mean pain score with exact 95% CIs will be presented for each assessment time point and lesion location. In case of both illumination fields have same location, pain of both illumination fields will be considered for tabulation. Additionally, mean of the maximum pain score (worst intensity) over all timepoints with exact 95% CIs for each lesion location will be presented. In case of both illumination fields have same location, maximum pain score (worst intensity) of both illumination fields will be considered for tabulation.

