#### Vital signs (blood pressure, heart rate)

Blood pressure (systolic and diastolic) and pulse rate will be analyzed using descriptive statistics by time point. In addition, absolute changes from baseline will be displayed by time point.

The absolute change from baseline to a visit will be calculated by the observed value at the respective visit minus the baseline value for non-missing observations.

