### 4.9 Miscellaneous

For qualitative variables the frequencies (absolute and relative) are calculated. If no further remark is given in the description of the tables the following format will be used for all tables with qualitative variables (total will only be calculated if appropriate):

	Y-variable(s) (e.g., treatment group)						
	Category 1		Categ	Category 2		Total	
X-variable(s)	N	%	Ν	%	Ν	%	
category 1	XX	XX.X	XX	XX.X	XX	XX.X	
category 2	XX	XX.X	XX	XX.X	XX	XX.X	
Total	ХХ	100.0	XX	100.0	XX	100.0	

For this standard format the description of the tables in Appendix A determines only the X- and Yvariables. If another format of table is described in the details to the tables, the real design will be determined by the technical possibilities within SAS/STAT® software and may not look identical to the provided example. However, all information as displayed will be included.

Quantitative parameters will be described by declaring the mean value, standard deviation, minimum, first quartile, median, third quartile, maximum, and number of non-missing observations. In the description of the tables this will be denoted by "basic statistics".

The listings are always sorted by treatment group, center, and subject. If a different sorting order should be used for some listings this will be remarked separately. The variables for the special listings are explicitly given in the description of listings.

Enrolled but not treated subjects (e.g. withdrawal before treatment) will be considered in tables and listings describing disposition of subjects, analysis sets and discontinuation as well as listings for subject demographics, and time schedules.

The following title will be used for all generated tables, listings, and graphs:

ALA-BCC-CT013: Phase III trial with BF-200 ALA/BF-RhodoLED in the treatment of sBCC Page # of #

 <Subtitle for description of contents - if applicable> <Analysis set>

The numbering NNN of the tables/listings/graphs will be stated in the detailed description (Appendix A).

The following footnote will be used for all generated tables, listings, and graphs:

Program: <Name of program> Run date/time: <Actual date(yyyy-mm-ddThh.mm)>

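### The SAP specifies the illumination pain score only by lesion location, omitting without declaration the all-location mean and maximum per time point and treatment group that the protocol promises

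*SAP*

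**What the plan says.** Protocol 11.3.4 commits to this for the numeric rating pain scale (NRPS): "The mean and the maximal pain score and the respective CIs will be presented for each assessment time point and treatment group". Location is not mentioned.

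SAP 4.5, Pain, specifies two summaries:

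- For the mean: "The mean pain score with exact 95% CIs will be presented for each assessment time point and lesion location".
- For the maximum: "mean of the maximum pain score (worst intensity) over all timepoints with exact 95% CIs for each lesion location will be presented".

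If a subject's two illumination fields lie in the same location, both scores enter the first summary. For the second, the larger of the two is used.

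The neighbouring paragraph on local discomfort has a summary that "will be presented by category and for each assessment time point" before it turns to location. The pain paragraph has no such sentence.

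SAP section 5 lists four items: local skin reactions, the TEAE definition, small wording adaptations and the satisfaction scale. The pain score is not among them. The local skin reaction entry concerns the protocol sentence immediately before the pain sentence, so a departure in that same paragraph was treated as reportable.

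**The concern.** Pain during illumination is a named safety variable in both documents, and Protocol 1.1 calls it a common side effect of PDT. The natural summary is one NRPS figure per session and arm, which is what the protocol promises. The SAP text puts in its place a set of location-specific figures and a maximum that no longer refers to a session.

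Three things follow if the SAP is programmed as written:

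- The smaller arm is divided among body areas, with a loss of precision and no pooled figure to fall back on.
- A subject with two fields in one location contributes two correlated scores to one mean. No subject-level rule is given for its interval.
- The maximum over all sessions depends partly on how many sessions a subject received, and that number is tied to response and hence to arm.

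**Working it through.** **Inputs.** The arm sizes are 149 and 37 (SAP 1.1). There are four body areas: face/forehead, bald scalp, neck/trunk and extremities (Protocol definitions). The scale runs from 0 to 10. The documents give no SD for pain and no location distribution, so both are assumed and varied below. The SAP calls the interval exact without naming a method; a t interval is used here.

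**The plan's own figure.** The documents state no precision for pain. The 37 vehicle subjects come from the primary sample size, which reproduces. The pooled rate is (149×0.65 + 37×0.25)/186 = 0.570. The standard errors are √[0.570×0.430×(1/149 + 1/37)] = 0.0909 under the null and √[0.65×0.35/149 + 0.25×0.75/37] = 0.0812 under the alternative. Then (0.40 − 3.090×0.0909)/0.0812 = 1.47, a power of 92.9%. With a continuity correction it is 89.6%. The stated value is at least 90%.

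**Precision of the vehicle mean at one session.** Half-width = t(0.975, n−1) × SD/√n. At SD 2, n = 37 gives 2.028×2/√37 = 0.67, and n = 9 (37/4 = 9.25, an even split) gives 2.306×2/√9 = 1.54. The ratio is 2.3 for any SD.

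| Vehicle subjects in the cell | SD 1.5 | SD 2 | SD 2.5 | SD 3 |
|---|---|---|---|---|
| 37 (all locations) | 0.50 | 0.67 | 0.83 | 1.00 |
| 18 | 0.75 | 0.99 | 1.24 | 1.49 |
| 9 (even split) | 1.15 | 1.54 | 1.92 | 2.31 |
| 4 | 2.39 | 3.18 | 3.98 | 4.77 |
| 2 | 13.5 | 18.0 | 22.5 | 27.0 |

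An illustrative uneven split of 10/5/50/35% gives about 4, 2, 18 and 13 vehicle subjects. At SD 2 the two large cells have half-widths of 0.99 and 2.179×2/√13 = 1.21, which are usable. The cell of 4 has 3.18, and the interval for the cell of 2 is wider than the scale.

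**Precision of the arm difference, 4:1.** Half-width = t × SD × √(1/n + 1/(4n)), with n vehicle subjects. At SD 2 this is 0.73 for n = 37, 1.50 for n = 9 and 2.35 for n = 4.

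**Double counting.** Protocol 7.3.1 allows up to two illumination areas and describes them as lying within one treatment area. For a subject with two fields, a shared location may therefore be common. The documents do not say how many subjects will have two fields, so the effect on the interval cannot be sized.

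**Number of sessions.** A maximum over four sessions cannot be lower than the maximum over the first two of them. Only subjects with remaining lesions at Visit 5 receive PDT-3 and PDT-4 (Protocol 5.1.2). The planned response rates are 65% and 25%, so more four-session subjects are expected on vehicle. Those rates are for the composite endpoint after the last cycle, not for the clinical assessment that triggers retreatment. They support the direction, not a size. The collapsed maximum could narrow the contrast between arms for a reason unrelated to pain per session.

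**The case against.** The strongest reply is that little is lost and that no decision depends on it. Four parts of it stand.

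- A reader might infer that the comparison by arm has been dropped. It has not. SAP 3.7 has every analysis on the safety set done by treatment received, and SAP 4.5 puts all safety analyses on that set. The pain paragraph does not repeat this, and neither does the one on vital signs, which "will be analyzed using descriptive statistics by time point".
- A reader might infer that pain is reported only by body location. That is true of the NRPS score, not of pain. Protocol 7.3.2 says "the NRPS result indicated by the subject should be transformed for documentation in the AE eCRF page as follows" (1–3 mild, 4–7 moderate, 8–10 severe), and the SAP tabulates TEAEs "displaying the number of events as well as counts and percentages on a subject basis per treatment arm", and also by intensity. Local reactions are further tabulated by intensity for each PDT cycle. None of these tables is split by body location.
- The layout is not fully visible. SAP 4.9 says that for standard-format tables "the description of the tables in Appendix A determines only the X- and Yvariables", and that appendix is not in the supplied text. A total row may exist there, or time point and location may be two separate breakdowns.
- All safety analysis is descriptive. No test or decision rule uses this table.

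This narrows the point without removing it. Three severity grades by preferred term or by cycle do not give a mean score with an interval per session. Even if time point and location are separate breakdowns, the maximum per time point is still absent from the text, and so is a rule for subjects with two fields.

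**Conclusion.** The point holds as an undeclared omission in a descriptive safety table. The SAP text specifies no NRPS mean or maximum pooled over locations, per session and arm, although Protocol 11.3.4 promises both. It replaces the per-session maximum with one over all sessions, and section 5 is silent.

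The size is a loss of precision of about 2.3-fold for the vehicle mean under an even split over four areas: 0.67 to 1.54 points at SD 2, within a range of 0.50 to 1.15 (SD 1.5) up to 1.00 to 2.31 (SD 3). These figures assume that all 37 vehicle subjects are treated at the session, and they rest on an SD and a location mix that the documents do not give.

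Two stronger readings are not supported. One is that the location cells are uninformative: at about 9 subjects they are wide but readable on a 0–10 scale, and only rare locations become unusable. The other is that pain is the trial's main tolerability outcome: both documents list it among several safety variables without ranking them.

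The priority is low, but the correction is specific and cheap.

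**What to change.** Add to SAP 4.5, Pain: for each PDT session and treatment group, on subjects treated at that session, present the mean and the maximal NRPS score with 95% CI, pooled over locations, using one value per subject per session (for example, the maximum over illumination fields). State the interval method, and state which quantity the interval for the maximal score refers to, since the protocol sentence leaves that open. A mean of per-subject maxima alone would not be enough, because the protocol promises both the mean and the maximal score.

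Keep the by-location tables as supplementary, and list any remaining departure from Protocol 11.3.4 in SAP section 5. If Appendix A already contains the pooled table, the text of 4.5 only needs to say so and to give the one-value-per-subject rule.

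The cost is one extra table. The scores are already collected per session and field, so no new data are needed.

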#### Vital signs (blood pressure, heart rate)

Blood pressure (systolic and diastolic) and pulse rate will be analyzed using descriptive statistics by time point. In addition, absolute changes from baseline will be displayed by time point.

The absolute change from baseline to a visit will be calculated by the observed value at the respective visit minus the baseline value for non-missing observations.

#### Safety laboratory assessments

All details regarding laboratory assessments will be listed. In addition, a listing of clinically significant values will be provided.

#### Physical examinations

General physical examinations will include the following body systems: heart, lung, abdomen, nervous system, skin, musculoskeletal system, lymph nodes, limbs, head, ears, eyes, nose, throat, and others. All clinically significant abnormal physical findings will be listed.

## 4.6 Missing Values

Missing values for the primary and secondary endpoints will be imputed as follows:

For all subjects missing values for the primary and secondary endpoints for the first PDT cycle will be imputed as follows:

- For the analysis of the composite endpoint clinical and histological response of the Main Target Lesion a missing clinical and/or histological lesion assessment of the Main Target Lesion on Visit 5 will be considered as non-response.
- For the analysis of histological response only a missing histological lesion assessment of the Main Target Lesion on Visit 5 will be considered as non-response.
- For the analysis of clinical response only of the Main Target Lesion as well as for the clinical response of Additional Target Lesions a last observation carried forward (LOCF) approach will be used to impute clinical assessments on Visit 5: If the clinical assessment of lesion clearance (yes/no) on week 12 after PDT-1 (i.e. Visit 5) is missing but week 5 after PDT-1 (i.e. Visit 4) assessment is available, missing week 12 after PDT-1 data will be imputed by week 5 after PDT-1 data. If a lesion clearance is not assessed on week 5 after PDT-1 and on week 12 after PDT-1, the lesion will be regarded as non-responder on Visit 5. Lesions with missing clinical assessments on Visit 4 will be regarded as non-responders.

For partial/non-responders at Visit 5 or subjects imputed as partial/non-responders at Visit 5 missing values for the primary and secondary endpoints for the second PDT cycle will be imputed as follows:

- For the analysis of the composite endpoint clinical and histological response of the Main Target Lesion a missing clinical and/or histological lesion assessment of the Main Target Lesion on Visit 8 will be considered as non-response.
- For the analysis of histological response only a missing histological lesion assessment of the Main Target Lesion on Visit 8 will be considered as non-response, if the Main Target Lesion was not already clinically cleared and excised at Visit 5. If the Main Target Lesion was already clinically cleared and excised at Visit 5, the histological lesion assessment of the Main Target Lesion at Visit 5 will be carried forward to Visit 8 following a last observation carried forward (LOCF) approach.
- For the analysis of clinical response only of the Main Target Lesion as well as for the clinical response of Additional Target Lesions a last observation carried forward (LOCF) approach will be used to impute missing clinical assessments: If the clinical assessment of lesion clearance (yes/no) on week 12 after PDT-3 (i.e. visit 8) is missing but week 5 after PDT-3 (i.e. visit 7) assessment is available, missing week 12 after PDT-3 data will be imputed by week 5 after PDT-3 data. If a lesion clearance is not assessed on week 5 after PDT-3 and on week 12 after PDT-3, the lesion will be regarded as non-responder on Visit 7 and Visit 8.
- For complete responders after cycle 1 who by mistake received a second treatment cycle, evaluations of the 1st cycle will be considered for all efficacy analyses, including the primary analysis.
- No replacement of missing values will be done for the secondary endpoints assessment of esthetic appearance by the investigator and subjects' satisfaction regarding esthetic outcome.

No additional methods on replacement of missing values of efficacy variables will be applied.

As sensitivity analysis for the primary and selected secondary efficacy variables additionally a complete cases analysis will be done.

Missing values of safety variables will not be replaced.

